If prolonged myelosuppression (more than 8 weeks) WITH evidence of a hypocellular marrow (marrow cellularity less than 5% without evidence of leukemia) is observed, 5-azacytidine and nivolumab OR 5-azacytidine with nivolumab and ipilimumab OR 5-azacytidine with nivolumab and venetoclax will be discontinued. Delays in start of subsequent cycles greater than 8 weeks will be acceptable only for patients who are deriving clinical benefit and after discussion with the principal investigator of potential risk/benefit ratio. If the peripheral counts do not recover (ANC <1 x10⁹/L and/or platelets <30 x10⁹/L) but there is evidence of residual leukemia in the bone marrow by morphology or flow-cytometry, subsequent cycles can be administered at the discretion of the treating physician not earlier than 21 days after the prior cycle.

5.2.2.5 For patients who discontinue therapy, the reason for treatment discontinuation will be captured.

5.2.2.6 Patients must receive at least 5 of 7 planned doses of azacitidine, 2 of 2 planned doses of nivolumab and 18 of 21 planned doses of venetoclax during the first 28 days on trial (i.e. during cycle 1) to be considered evaluable

Nivolumab and azacytidine during the DLT phase. Patients who receive less than these doses of each drug during the first 28 days on trial will not be considered evaluable during the DLT phase. However, if such patients develop a toxicity that would normally be considered a DLT this will still be captured as a DLT. Any toxicity that meets the criteria for DLT during the first 28 days of trial in a patient who has received at least one dose of either azacitidine, venetoclax or nivolumab will constitute a DLT. Patients not considered evaluable due to insufficient dosing and who do not develop a toxicity that is considered a DLT will be replaced. These patients may continue therapy on trial after discussion with the PI if they are having clinical benefit and the reasons for continuation and potential benefit/risk profile for the patient must be clearly documented in the medical records. In the expansion phase (part b), DLT will not be monitored. We will perform continuous safety monitoring every 5 patients for “drug-related non-hematological Grade 3/4 AE’s.”

5.2.2.7 Dose modifications other than the ones mentioned above can be considered after discussion with the PI and proper documentation of the rationale.

5.2.2.8 Clinical trial update: The safe dose of 5-azacytidine and nivolumab has been established as 5-azacytidine 75mg/m² days 1-7 and nivolumab 3.0 mg/kg on days 1 and 14 of each cycle in the ongoing clinical trial. 1/6 patients experienced a DLT at this dose during the safety-run-in phase. All subsequent patients (including relapsed/refractory AML and newly diagnosed elderly AML) will receive this dose of 5-azacytidine and nivolumab. For the 5-azacytidine with nivolumab and ipilimumab the MTD established from the run-in phase will be used to treat both salvage and frontline patients. For the 5-azacytidine with nivolumab and venetoclax the MTD/RP2D established from the lead-in part a (Table 5C) will be used to treat both salvage patients and frontline patients in the expansion part B: see “statistics” section for more details.

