- Grade 3 or 4 nausea, vomiting and diarrhea will be considered DLT only if not controlled by optimal therapy.
- Grade 3 biochemical abnormalities (e.g., lipase or bilirubin elevation) will only be considered DLT if accompanied by clinical consequences. Grade 3 or 4 electrolyte abnormalities will only be considered DLT if possibly related to study drug and not corrected by optimal replacement therapy.
- Results in discontinuation of therapy
- Any treatment-related death;

Hematologic DLT is defined as grade ≥ 3 neutropenia and/or thrombocytopenia with a hypocellular bone marrow ($<10\%$ cellularity) lasting for 42 days or more from Cycle 1 Day 1 in the absence of residual leukemia (i.e., with less than 5% blasts or residual leukemia by flow-cytometry or RT-PCR). Anemia will not be considered for the definition of DLT.

-Patients that are removed from study before day 28 for any reason other than toxicity and have not experienced DLT will be replaced. Patients who come off study earlier than 28 days during the DLT evaluation period may continue to receive protocol therapy if they are having clinical benefit, after discussion with the PI. The rationale for continuing therapy must be clearly documented in the patients chart.

-Patients who do not receive venetoclax on day 1 due to logistical and/or financial reasons, the DLT period will be extended to 28 days from the first dose of venetoclax. For evaluation of neutropenia-related DLT, the DLT period will be 42 days from the first dose of venetoclax.

5.2.1.5 Arm 1: We will first treat 6 patients at dose level 0 in the lead-in phase. If DLT occurs in $>/=2/6$ patients, this dose level would exceed the MTD, and 6 patients will be treated at the next lower dose level (i.e. dose level -1). The dose de-escalation (Table 5) will continue in cohorts of 6 until we reach a dose level at which $<2/6$ patients experience a DLT in the first 28 days. The dose level at which 0-1/6 patients experience a DLT in the first 28 days of treatment will be the MTD and will be used to treat an additional patients in the phase II portion of the study. If $>/=2/6$ patients experience DLT at dose level -4, the study will be revised to consider additional lower dose levels (based on potential synergistic toxicity).

If DLT is observed in the first 28 days of treatment in 0 or 1/6 at dose level 0, then dose level 0 will be used for the phase II portion of the study.

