Patients that are removed from study before day 28 for any reason other than toxicity and have not experienced DLT will be replaced.

5.2.1.6 Arm 2: We will first treat 6 patients at dose level 0 in the lead-in phase. If DLT occurs in $>/=2/6$ patients, this dose level would exceed the MTD, and 6 patients will be treated at the next lower dose level (i.e. dose level -1). If DLT occurs in $</=1/6$ patients, this dose level would not exceed the MTD, and 6 patients will be treated at the next higher dose level (i.e. dose level +1). The dose escalation or de-escalation (Table 5b) will continue in cohorts of 6 until we reach a dose level at which $<2/6$ patients experience a DLT in the first 28 days or if $</=1/6$ patients experience a DLT at dose level +1. The highest dose level at which 0-1/6 patients experience a DLT in the first 28 days of treatment will be the MTD and will be used to treat an additional 54 salvage 1 and 2 patients (Arm 2 Salvage Cohort) and 30 frontline AML $>/= 65$ years not candidates for induction therapy (Arm 2 Frontline cohort) in the phase II portion of the study. If $>/=2/6$ patients experience DLT at dose level -2, the study will be revised to consider additional lower dose levels (based on potential synergistic toxicity).

Patients that are removed from study before day 28 for any reason other than toxicity and have not experienced DLT will be replaced.

5.2.1.7 Arm 3: We will first treat 6 patients at dose level 0 in the lead-in phase (part a). If DLT occurs in $>/=2/6$ patients, this dose level would exceed the MTD, and 6 patients will be treated at the next lower dose level (i.e. dose level -1). The dose de-escalation (Table 5C) will continue in cohorts of 6 until we reach a dose level at which $<2/6$ patients experience a DLT in the first 28 days. The dose level at which 0-1/6 patients experience a DLT in the first 28 days of treatment will be the MTD. If $>/=2/6$ patients experience DLT at dose level -3, the study will be revised to consider additional lower dose levels (based on potential synergistic toxicity).

If DLT is observed in the first 28 days of treatment in 0 or 1/6 at dose level 0, then dose level 0 will be the MTD. The RP2D will be selected at the end of the lead-in phase and may be the MTD dose or a dose level lower than the MTD.

Patients that are removed from study before day 28 for any reason other than toxicity and have not experienced DLT will be replaced.

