- Venetoclax will be administered orally daily on Days 1-21 of the first cycle; and Days 1-14 for subsequent cycles.
- In cycle 1, patients should undergo a bone marrow aspiration and biopsy on day 21 (+/- 4 days). Patients who achieve marrow remission (i.e. bone

Nivolumab and azacytidine marrow blasts <5% by morphology) or marrow aplasia/hypoplasia (</=10% cellularity or insufficient sample) should discontinue venetoclax for the remainder of the cycle and be monitored for count recovery.

- a) If the Day 21 bone marrow shows <5% blasts, the venetoclax should be held, and cycle 2 should not be initiated till ANC>0.5 and platelets are >30K without platelet transfusion support for >5 days.
- b) If the Day 21 bone marrow shows aplasia/hypoplasia (</=10% cellularity or insufficient sample), the venetoclax should be held on Day 21, and a repeat bone marrow should be performed on Day 28 (+/- 4 days) for response and MRD assessment. If the Day 28 bone marrow shows >/=5% blasts proceed with cycle 2 if this is in the best interest of the patient (those with C1D28 bone marrow >/=5% are allowed to receive 21 days of venetoclax in cycle#2). If the Day 28 bone marrow shows <5% blasts, the venetoclax should continue to be held, and cycle 2 should not be initiated till ANC>0.5 and platelets are >30K without platelet transfusion support for >5 days. If the Day 28 bone marrow shows persistent aplasia/hypoplasia (</=10% cellularity or insufficient sample) continue to hold the venetoclax and repeat a bone marrow in approximately 10-14 days.
- c) If a bone marrow remission (<5% blasts) or aplasia/hypoplasia is not confirmed on the Day 21 bone marrow, patients should continue venetoclax until day 28 and have a repeat bone marrow on Day 28 (+/- 5 days). If the Day 28 bone marrow shows >/=5% blasts proceed with cycle 2 if this is in the best interest of the patient (those with C1D28 bone marrow >/=5% are allowed to receive 21 days of venetoclax in cycle #2). If the Day 28 bone marrow shows <5% blasts or aplasia/hypoplasia follow steps outlined in "a" and "b" above.
- d) Treatment interruptions and dosing schedules other than the ones mentioned above can be considered after discussion with the PI and proper documentation of the rationale.
- e) Of note the nivolumab infusion will continue as scheduled and will not be impacted or adjusted based on venetoclax dosing schema or venetoclax related delays.

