- During cycle 1, venetoclax will be dose escalated daily to the goal dose of 400mg daily. Patients will receive 100mg on Day 1, 200mg on Day 2 and 400mg on Day 3 and onwards, or adjusted dose if on concomitant azoles (discussed below in section 6.3). Venetoclax dose ramp-up as described in section 6.4.
- If venetoclax is not available at the start of therapy due to different reasons (insurance, financial, transportation, others), azacitidine and nivolumab can start and venetoclax is added when it becomes available.
- If azacitidine cycles are delayed, venetoclax therapy may continue on Days 1-21 of a 4-week cycle after discussion with the PI or Co-PI and documentation in the medical record. If azacitidine cycles are delayed, nivolumab may continue as scheduled (q2 weeks) after discussion with the PI or Co-PI and documentation in the medical record.

5.2.2 One cycle of therapy is defined as 28 days. Patients will receive one cycle of therapy every 28 days (+/- 7 days). The ipilimumab will be given every 6 weeks (+/-3 days).

5.2.2.1 In the expansion (part b) portion of the study (once the MTD/RP2D dose has been defined) cycles may be started early (but not earlier than day 21) for patients with active disease if judged in the best interest of the patient.

Nivolumab and azacytidine

For the lead-in (part a) cohort, DLT defining period is 28 days. As such, cycle 2 should not be started before 28 days for the patients being treated on the lead-in cohort.

5.2.2.2 Subsequent cycles may be delayed for recovery of toxicity or other medical conditions (e.g. infections). Delays in start of subsequent cycles greater than 8 weeks will be acceptable only for patients who are deriving clinical benefit and after discussion with the principal investigator of potential risk/benefit ratio.

5.2.2.3 In instances where one drug has to be discontinued transiently because of safety, the administration of the other drug may continue as scheduled. If the drug that is held can resume at a later time, no doses will be made up and the administration will follow the originally defined schedule calendar according to the drug that was continued.

5.2.2.4 Subsequent courses of 5-azacytidine and nivolumab OR 5-azacytidine with nivolumab and ipilimumab OR 5-azacytidine with nivolumab and venetoclax may be administered regardless of peripheral blood counts during the first 4 cycles and/or in the presence of residual leukemia.

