11.3 Statistical Design

Part a. Lead-in phase

The MTD is defined as the highest dose level with < 2 out of 6 patients experience a DLT during the first 28 days of treatment. DLT is defined in section 5.2.2. The dosing schema for the combination treatment during the lead in phase is shown in Tables 5 and 5B in section 5.2.1.

Part b. Expansion phase

A. Arm 1 Relapsed/Refractory AML cohort (Aza+Nivo) (N=70: completed accrual and closed to accrual)

Historical data on similar patients show a ORR of 10-15%. The target ORR with the experimental treatment is 30%. This regimen of the combination treatment will be considered worthy of further investigation if it elicits an increase in ORR to 30% with acceptable toxicity. A >30% drug-related grade 3/4 toxicity rate is considered unacceptable. Thus, interim monitoring rules, assuming the prior distributions below, were constructed that meet the following two conditions,

- 1) Stop if $\text{Prob}\{ p(\text{ORR}, E) < p(\text{ORR}, H) + 0.15 \mid \text{data} \} > 0.99$, or
- 2) Stop if $\text{Prob}\{ p(\text{TOX}, E) > 0.30 \mid \text{data} \} > 0.95$,

Where $P(\text{ORR}, E)$ and $P(\text{TOX}, E)$ are the true ORR and toxicity rates for the combination treatment, and $p(\text{ORR}, H)$ is the true ORR rate of the standard treatment. The first rule provides for stopping the study if the data suggest that it is unlikely (i.e., probability < 1%) that ORR rate of the combination treatment is greater than the ORR rate of standard treatment by 15.0%. The second condition will stop the study early if excessive therapy-related grade 3/4 toxicity (>30%) is highly probable (i.e., probability >95.0%) for the combination treatment. Monitoring for toxicity and futility will not begin until 6 patients have been evaluated, and cohort size for future evaluations is 3.

The monitoring rule for the toxicity rate, based on these assumptions and monitoring conditions above is found in Table 9. **For example, accrual will cease if 5 or more patients experience toxicities among the first 6 patients.**

| |
|--|
| Table 9. Stop accrual if the number of drug-related grade 3/4 toxicities is greater than or equal to indicated (i.e., # patients with toxicities) among the number of patients evaluated |
|--|

Nivolumab and azacytidine

| # patients evaluated | 3 | 6 | 9 | 12 | 15 | 18 | 21 |
|----------------------------|-------|-------------------------------------|-------|-------|-------|-------|-------|

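### Arm 3 lead-in: the MTD rule counts DLTs to day 28, but a haematologic DLT takes 42 days to establish, and no text says which governs

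*Combined protocol and SAP*

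**What the plan says.** The haematologic DLT definition follows Table 5C in section 5.2.1.4. It requires grade 3 or worse neutropenia and/or thrombocytopenia with marrow cellularity below 10%, "lasting for 42 days or more from Cycle 1 Day 1 in the absence of residual leukemia".

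Four places use a 28-day window:

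- Section 5.2.1.7 (Arm 3): "The dose level at which 0-1/6 patients experience a DLT in the first 28 days of treatment will be the MTD". The same section repeats the 28-day condition for dose level 0.
- Section 11.3, part a: the MTD is the "highest dose level with < 2 out of 6 patients experience a DLT during the first 28 days of treatment".
- Section 5.2.2.1: "For the lead-in (part a) cohort, DLT defining period is 28 days".
- Section 5.2.2.6, the capture rule: "Any toxicity that meets the criteria for DLT during the first 28 days of trial" counts as a DLT once the patient has had at least one dose of any of the three drugs.

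The replacement rule has the same limit: "Patients that are removed from study before day 28 for any reason other than toxicity and have not experienced DLT will be replaced". The end of section 11.3 asks for the lead-in review when six evaluable patients have finished cycle 1, and section 5.2.2 sets a cycle at 28 days.

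Other text points towards a longer window. The goal sentence under Table 5C and the first de-escalation trigger in 5.2.1.7 (two or more of six with a DLT) give no day limit. Section 3.1 makes the lead-in cycle a minimum of 28 days. The bullet in 5.2.1.4 on delayed venetoclax adds: "For evaluation of neutropenia-related DLT, the DLT period will be 42 days from the first dose of venetoclax".

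**The concern.** Finding the MTD and DLTs of the triplet is a primary objective (section 1.1, part a, item 3). The protocol defines a DLT for that purpose which, for a patient who starts venetoclax on time, cannot be established inside the window that declares the MTD. If the team applies the 28-day sentences, prolonged marrow aplasia does not enter the two-of-six count. If it applies the sentences without a day limit, it does. The same six patients can give different answers, and nothing in the plan settles which is right.

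Marrow toxicity is relevant to this arm. Section 5.6 names azacitidine and venetoclax as causes of myelosuppression. The Arm 3 rationale in section 2.6 expects that adding nivolumab may not bring severe or prolonged cytopenia. The lead-in is the natural place to test that expectation, and two expansion cohorts of 30 follow at the selected dose.

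**Working it through.** **1. The plan's own figure.** Section 11.2 gives a lead-in maximum of 18. Three dose levels × 6 patients = 18, which agrees. The plan gives no operating characteristics for the two-of-six rule, so there is no stated probability to reproduce.

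**2. The two windows, for a patient starting venetoclax on Cycle 1 Day 1.**

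| Element | Window | Section |
|---|---|---|
| Haematologic DLT definition | 42 days or more | 5.2.1.4 |
| MTD declaration | first 28 days | 5.2.1.7, 11.3 |
| DLT-defining period | 28 days | 5.2.2.1 |
| Capture rule | first 28 days | 5.2.2.6 |
| Replacement rule | before day 28 | 5.2.1.4, 5.2.1.7 |
| MTD goal; first de-escalation trigger | no day limit | 5.2.1.4, 5.2.1.7 |
| Late venetoclax, neutropenia only | 42 days from first venetoclax dose | 5.2.1.4 |

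Gap: 42 − 28 = 14 days. A cytopenia may begin before day 28, but its required duration is not reached by then.

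**3. How the rules collide.** Suppose level 0 has one non-haematologic DLT by day 28, and a second patient reaches day 42 with aplasia that meets the definition. At day 28 the count is 1 of 6, so level 0 is the MTD. At day 42 it is 2 of 6, and under the trigger without a day limit level 0 exceeds the MTD. No sentence ranks the two results or delays the first.

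**4. Timing of the marrow that would establish the event.** When the day-28 marrow is still aplastic, 5.2.1.7 says to "continue to hold the venetoclax and repeat a bone marrow in approximately 10-14 days". That is day 28 + 10 = 38 to day 28 + 14 = 42. With the ±4-day window in step b it is 24 + 10 = 34 to 32 + 14 = 46. With the ±5-day window in step c it is 23 + 10 = 33 to 33 + 14 = 47. All of these fall after day 28.

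**5. Illustration only.** Let q be the non-haematologic and h the haematologic DLT rate per patient. Both are assumed, and the events are taken as independent. The dose is accepted if X ≤ 1, with X ~ Binomial(6, p) and P(X ≤ 1) = (1 − p)^6 + 6p(1 − p)^5. Here p = q if haematologic DLTs are not counted, and p = 1 − (1 − q)(1 − h) if they are.

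| q | h | p with both counted | Accept, q only | Accept, both |
|---|---|---|---|---|
| 0.05 | 0.05 | 0.0975 | 0.967 | 0.891 |
| 0.05 | 0.10 | 0.145 | 0.967 | 0.788 |
| 0.05 | 0.20 | 0.24 | 0.967 | 0.558 |
| 0.10 | 0.05 | 0.145 | 0.886 | 0.788 |
| 0.10 | 0.10 | 0.19 | 0.886 | 0.680 |
| 0.10 | 0.20 | 0.28 | 0.886 | 0.464 |
| 0.20 | 0.05 | 0.24 | 0.655 | 0.558 |
| 0.20 | 0.20 | 0.36 | 0.655 | 0.301 |

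In these rows the difference runs from 0.967 − 0.891 = 0.076 to 0.886 − 0.464 = 0.422. It depends almost wholly on h, which the documents do not give.

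**The case against.** A reader might infer that the plan leaves haematologic DLTs out of the MTD decision. The documents do not support that. No sentence excludes them, and section 5.2.1.4 defines them as DLTs for this lead-in. The MTD goal and the first Arm 3 trigger have no day limit, and the late-venetoclax bullet suggests that the authors had 42 days in mind.

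The timing may also be looser than 28 days. Section 3.1 sets a minimum cycle length. Section 5.2.1.7 bars cycle 2 in patients with fewer than 5% blasts until counts recover, and section 5.3 lets a cycle run on if azacitidine is delayed. A patient heading for a haematologic DLT may still be in cycle 1 when the review is prepared.

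The consequences are limited too. Level 0 is both the starting and the target dose, so Arm 3 can only de-escalate. The recommended phase II dose may lie below the MTD. The medical monitor reviews each cohort (5.2, 11.3), and the aplasia steps in 5.2.1.7 protect individual patients whatever the counting window. The step from level 0 to −1 lowers only nivolumab, which section 5.3.1 says has not been associated with neutropenia or thrombocytopenia. Counting a haematologic DLT would first reduce the drug least suspected.

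All of this stands as a limit on severity. It does not remove the conflict. The sentences that declare the MTD still say 28 days, section 5.2.2 still defines a cycle as 28 days, the 42-day sentence omits thrombocytopenia and sits in a bullet about late starts, and the safeguards are discretionary or apply to one patient at a time.

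**Conclusion.** The Arm 3 MTD rule and the haematologic DLT definition are not reconciled. Followed literally, the 28-day sentences can accept a dose level that the protocol's own DLT definition, applied at day 42, would reject. The textual finding is a 14-day mismatch and needs no assumption beyond venetoclax starting on Cycle 1 Day 1.

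It should be fixed because the rule serves a primary objective and the repair is cheap. It does not show that an unsafe dose would be chosen: the arm only de-escalates, the selected dose may be lower than the MTD, and cohort review and the aplasia steps remain. The acceptance probabilities rest on assumed, independent DLT rates. They show the direction of the effect and how strongly it depends on the haematologic rate. They do not measure its size in this trial.

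**What to change.** For Arm 3 only, amend 5.2.1.7, 5.2.2.1, 5.2.2.6 and 11.3 as follows.

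1. Count non-haematologic DLTs to day 28 and all haematologic DLTs, thrombocytopenia as well as neutropenia, to day 42. Count from Cycle 1 Day 1, or from the first venetoclax dose if venetoclax starts late.
2. Hold the six-patient decision only while a patient who is cytopenic without leukaemia at day 28 has not yet recovered, met the DLT definition or reached day 42.
3. Replace such a patient who leaves between days 28 and 42 for a reason other than toxicity and without a DLT.

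The cost is protocol wording and, when the hold is triggered, up to about 14 days per cohort. If it were triggered at all three levels, that is 3 × 14 = 42 days of waiting. Each replacement patient adds enrolment time and a further 28 to 42 days of observation. The planned lead-in of 18 evaluable patients does not change. The repeat marrow for persistent aplasia is already in the plan at about day 38 to 42, so the main assessment needed is largely in place.

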In spite of the encouraging efficacy of HMA with venetoclax in newly diagnosed older AML who are not good candidates for cytotoxic induction therapy, the median CR/CRI durations are $\leq 11-12$ months and median 3-year OS is $<45\%$ (DiNardo CD et al, *Blood*. 2019 Jan 3;133(1):7-17) suggesting that there is room for improvement by further improving the durability of CR/CRI's and thereby improving median OS. Similarly, MRD-negative rates with HMA with venetoclax are 40-50% and these may be further improved by the addition of an effective and tolerable third agent, potentially translating into more durable response and improved OS.

The long-term outcomes of patients with poor-risk disease features remain poor. Among frontline older poor risk patients treated with HMA with venetoclax (defined as patients with TP53 and adverse cytogenetics) evaluated in both the MDACC internal data set (Shoukier M et al, *Journal of Clinical Oncology* 37, no. 15_suppl (May 20, 2019) 7034-7034) and in the multicenter phase Ib/II trial of HMA with venetoclax (DiNardo CD et al, *Blood*. 2019 Jan 3;133(1):7-17) the

CR/CRi rates were significantly lower at 45-47%, median response durations were <6 months, median OS was 6-9 months, and only 14% of the patients achieving CR/CRi became MRD-negative.

Venetoclax plus HMA in R/R AML: Several retrospective studies have been published evaluating the safety and efficacy of venetoclax plus an HMA in patients with R/R AML.

-A study from MD Anderson evaluated the outcomes of 43 patients with R/R myeloid malignancies (n=39, 91% with AML) who received venetoclax in combination with other agents (DiNardo CD et al, *American journal of hematology* 2018; **93**(3): 401-7). Thirty-one of the evaluated patients (72%) received venetoclax with an HMA. Most patients (84%) were treated in salvage 2 or later (range 2-8) with a median of 3 prior treatment regimens. Objective response rate (ORR) was achieved in 9 (21%) patients, including 2 (5%) with CR, 3 (7%) with CRi, and 4 (9%) with morphologic leukemia-free state (MLFS). Of the 9 responding patients, all responded within 1 cycle of venetoclax combination therapy. These nine responding patients included eight (26%) of the patients treated with an HMA combination. With a median follow-up of 3 months, the estimated 6-month OS rate was 24% and median OS was approximately 5 months.

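### The hematologic DLT definition contradicts itself on flow- or RT-PCR-positive marrows with under 5% blasts, and its 42-day duration conflicts with the 28-day MTD window

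*Combined protocol and SAP*

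**What the plan says.** Protocol section 5.2.1.4, after Table 5C, defines a hematologic DLT as grade 3 or higher neutropenia and/or thrombocytopenia with marrow cellularity under 10%, "lasting for 42 days or more from Cycle 1 Day 1", and "in the absence of residual leukemia (i.e., with less than 5% blasts or residual leukemia by flow-cytometry or RT-PCR").

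Leukemia is tested differently elsewhere:

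- Section 5.2.1.7 (Arm 3, Day 21 marrow) defines marrow remission as "marrow blasts <5% by morphology".
- Section 5.2.2.4 refers to "evidence of residual leukemia in the bone marrow by morphology or flow-cytometry".
- Section 5.3.1 has two versions. One bullet allows count-based adjustments when blasts are under 5% by morphology or flow. Another treats flow evidence of leukemia as disease still present.

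On timing, section 5.2.1.7 says: "The dose level at which 0-1/6 patients experience a DLT in the first 28 days of treatment will be the MTD". Section 11.3 uses the same 28 days, section 5.2.2.1 gives 28 days as the DLT period for the lead-in, and section 5.2.2.6 captures DLT-level toxicity over the first 28 days. The one longer period is in the 5.2.1.4 bullet on patients who start venetoclax late: "For evaluation of neutropenia-related DLT, the DLT period will be 42 days from the first dose of venetoclax".

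**The concern.** The bracket is meant to explain when leukemia is absent, but it names residual leukemia by flow or RT-PCR as one way of meeting that condition. It can be parsed in three ways. First, blasts under 5% are enough. Second, flow and RT-PCR must also be negative. Third, the 5% limit also applies to flow. An aplastic marrow with few blasts and detectable disease by flow or RT-PCR is a DLT on the first parse and exempt on the second.

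The cut-off is 2 of 6, so one or two such patients can decide whether a level is declared above the MTD. The decision still open is Arm 3, because sections 5.2.2.8 and 2.3 D report doses already selected for Arms 1 and 2. The Arm 3 dose then goes to 30 + 30 = 60 expansion patients. Later rules are less likely to pick up a misclassified aplasia. Section 5.2.2.6 says that DLTs are not monitored in expansion and that continuous safety monitoring there covers non-hematologic events. Section 10.3 keeps abnormal hematologic values out of the CRF and AE log. Section 5.3.9 also uses hematologic DLT to bar re-escalation, so the wording matters beyond the MTD call.

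**Working it through.** **1. Do other sections settle the reading?** Section 5.2.1.7 uses morphology alone, for holding venetoclax. Section 5.2.2.4 and one bullet of 5.3.1 count flow evidence as leukemia, for continuing treatment. The other 5.3.1 bullet puts a 5% limit on morphology or flow. On balance they lean towards flow positivity counting as leukemia. None concerns DLTs and none mentions RT-PCR.

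**2. Does a hematologic DLT enter the MTD count?** The event needs 42 days and the MTD rule looks at 28, so on the wording it cannot be complete in time: 42 − 28 = 14 days short. Section 11.3 asks for the lead-in summary once six evaluable patients have completed cycle 1, which may also fall before day 42.

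**3. Size, if day-42 events do count.** The plan gives no operating characteristics for the 6-patient rule, so there is no figure to reproduce. Inputs:

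- *h*, the rate of prolonged aplasia with under 5% blasts: assumed 5% to 30%; the documents give none.
- *m*, the share of those marrows positive by flow or RT-PCR. Section 2.3 E says "MRD-negative rates with HMA with venetoclax are 40-50" per cent, whose complement is 50-60%. For poor-risk frontline patients it says "only 14% of the patients achieving CR/CRi became MRD-negative", whose complement is 86%. A 30% share is added as a low case.
- Other DLTs: none at first.

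Broad reading (under 5% blasts suffices): DLT rate *h*. Narrow reading (flow and RT-PCR must also be negative): *h*(1 − *m*). With DLT rate *p*,

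P(2 or more of 6) = 1 − (1 − p)^6 − 6p(1 − p)^5.

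Every narrow-reading DLT is also a broad-reading DLT. The calls therefore differ only when the broad count is 2 or more and the narrow count is 0 or 1, and the probability of that is the difference between the two tail probabilities.

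Example, *h* = 20%, *m* = 50%. Broad: 1 − 0.2621 − 0.3932 = 0.345. Narrow, *p* = 0.10: 1 − 0.5314 − 0.3543 = 0.114. Difference: 0.230.

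| *h* | Broad | Narrow, *m* = 30% | *m* = 50% | *m* = 60% | *m* = 86% | Call differs, *m* = 30% | Call differs, *m* = 50-86% |
|---|---|---|---|---|---|---|---|
| 5% | 3.3% | 1.7% | 0.9% | 0.6% | 0.1% | 1.6% | 2.4-3.2% |
| 10% | 11.4% | 6.1% | 3.3% | 2.2% | 0.3% | 5.3% | 8.1-11.1% |
| 20% | 34.5% | 20.0% | 11.4% | 7.7% | 1.1% | 14.4% | 23.0-33.4% |
| 30% | 58.0% | 36.9% | 22.4% | 15.6% | 2.4% | 21.1% | 35.6-55.6% |

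**4. Sensitivity to other DLTs.** If a patient has another DLT with probability *d* = 10%, the rates become *d* + (1 − *d*)*h* and *d* + (1 − *d*)*h*(1 − *m*). For *m* of 50-86%, the calls then differ in 11-18% of cohorts at *h* = 10% and in 22-37% at *h* = 20%.

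**The case against.** The strongest reply is that the MTD rule is a 28-day rule. As written, a 42-day event is outside the count on either reading, and mending the bracket alone would not bring it in. This stands, and it makes every percentage above conditional. It does not defend the text: a 42-day DLT that can never be counted would serve no purpose, and the late-venetoclax bullet shows that a 42-day period was contemplated for at least some patients.

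A second reply is that the governing words require leukemia to be absent, and that the protocol treats flow positivity as leukemia where it uses that language. This has weight for flow. It leaves RT-PCR open, and also the 5% limit that section 5.3.1 applies to flow.

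A reader might infer that most prolonged aplasias would be affected. The documents do not support that. The MRD figures are frontline, while section 3.1 limits the Arm 3 lead-in to relapsed/refractory patients, and no MRD rate is given for them or for marrows under 10% cellular. The higher assumed aplasia rates are also demanding: section 2.6 (Rationale for study) puts relapsed/refractory remission rates with this backbone at 20-40%, so a 30% aplasia rate would be a large part of that.

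Nor does the plan present prolonged cytopenia as the main expected toxicity. The Arm 3 rationale argues that adding nivolumab may avoid it. Finally, MRD results may not exist for every case. Section 5.2.1.7(b) names MRD for the Day 28 repeat marrow, but not for the further repeat 10-14 days later.

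**Conclusion.** The definition is wrong as written. Its bracket contradicts the phrase it explains, and a flow- or RT-PCR-positive hypocellular marrow with under 5% blasts is classified in opposite ways. Whether any hematologic DLT enters the MTD count is also unresolved.

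The effect on the dose decision is conditional. It requires that day-42 events count, and its size depends on rates the documents do not give for this population. It is small if prolonged aplasia is rare and material if it approaches 20%. A reader might infer that the Arm 3 MTD call is bound to change, but the documents show only that it could. This should be corrected before the definition is used to classify a lead-in patient.

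**What to change.** The sponsor should:

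1. Replace the bracket with one unambiguous test that says whether marrows with under 5% blasts but positive by flow or by RT-PCR count as hematologic DLTs.
2. Reconcile that test with the leukemia wording in sections 5.2.1.7, 5.2.2.4 and 5.3.1, or state that those sections serve a different purpose.
3. Reconcile the 42-day definition with the 28-day window in sections 5.2.1.7, 5.2.2.1, 5.2.2.6 and 11.3, and say whether the 42-day period applies only after a late venetoclax start.
4. List MRD status, where available, beside each prolonged-aplasia case, so that the DLT count can be shown under both readings.

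Which clinical test and window to adopt is for the sponsor; none is recommended here. The cost is a small wording change and one extra column in the lead-in summary. The resulting DLT count may differ from the one that one of the current readings would give.
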